D.1.1 Overview and Design. The proposed pilot study is designed as a culture-directed versus empiric antibiotic strategy for patient-reported UTI symptoms in older women. (Figure 2) Over 12 months, we will recruit 70 women with rUTI. Following enrollment, patients will be randomized in a 1:1 ratio to one of two groups. Patients assigned to the culture-directed arm will await results of urine culture prior to potentially receiving antibiotics and those assigned to the empiric arm will be prescribed immediate antibiotics from an established list of commonly prescribed antibiotics. Participants will be sent electronic questionnaires after urine culture results and then weekly for a total of 4 weeks. The primary outcome is feasibility of trial defined as recruitment of 10% of eligible participants with 70% adherence to study protocol.

D.1.2 Recruitment and Subject Eligibility. Women age ≥65 years⁶¹ with diagnosis of recurrent UTI (rUTI) will be recruited from: 1) UPMC WCBPH faculty practices or 2) CTSI Pitt+Me® Research Registry. Eligibility criteria are listed in Table 2.

Rationale for Inclusion Criteria: We will include participants with patient reported recurrent UTI to allow for a pragmatic study design and generalizability. Additionally, our definition of patient reported UTI is like other RCTs evaluating non-antibiotic options as compared to antibiotic strategies for UTI treatment.^{43,62} We will exclude participants with features of complicated UTI in the setting of structural or functional abnormalities or instrumentation /catheterization^{4,63} Eligibility is limited to female biologic sex given the differential risk profile of males and females who experience recurrent UTIs.

D.1.3 Study procedures (Figure 2).

D.1.3.1 – Screening and Enrollment Procedures.

Information on the REDUCTION trial will be broadly disseminated in the University of Pittsburgh faculty practices at the WCBPH, through IRB approved brochures, social media ads, institutional (MWRI) and CTSI websites. Interested women will be encouraged to contact the research staff for more information. Women who meet eligibility criteria after screening will be provided a consent form via their preferred method (electronic or paper).

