- Those with a negative urine culture will not be prescribed antibiotics and will be followed per protocol.
- Those with a positive urine culture who *report persistent UTI symptoms* will be given antibiotics following the priority list above with consideration to reported antimicrobial sensitivities.
- Those with a positive urine culture who *report resolution of UTI symptoms* will not be given antibiotic

Empiric Antibiotic Treatment.

- Those with a negative urine culture will be told to stop antibiotics
- Those with a positive urine culture sensitive to the empiric antibiotic will be instructed to complete the full course of their antibiotics
- Those with a positive culture resistant to empiric antibiotic will be given an alternative antibiotic per antibiotic protocol and will be followed per protocol. If there are no oral antibiotic options with patient-specific and antimicrobial sensitivities, we will engage local infectious disease physicians for management as per standard clinical protocols.

[figure not shown]
D.1.6. Study follow-up assessments.

All participants will be followed with electronic surveys via Research Electronic Data Capture (REDCap) software, which is a browser-based, metadata-directed EDC software and workflow methodology for designing

clinical and translational research databases,⁷² on day 2-3 (after result of urine culture). To avoid limiting enrollment to only those with access to technology, our research coordinator can also call and administer the questionnaire by phone to ensure ability to access and complete electronic materials. Follow-up assessments will be completed weekly for a total of 4 weeks. These will include UTISA questionnaire,⁶⁸ antibiotic associated side effects, use of other symptom mitigating remedies, and adherence to assigned study arm.

Participants will be provided with a clinical line to call 24/7 with report of worsening symptoms which will be discussed with the PI, [name] for determination of antibiotic prescription and if participants report fevers or chills this will prompt an in-person evaluation in clinic during business hours or the emergency department after hours. If participants call to report new symptoms during the study course, a repeat urine culture will be obtained.⁷³ Given that these episodes could be considered either a recurrent or incompletely treated infection we plan to manage these per clinical care and not based on the participants initial study arm.

Figure 2: Study Flow Diagram

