For a larger trial, electronic surveys may significantly reduce research coordinator burden. To evaluate feasibility of this approach we will administer electronic surveys through Research Electronic Data Capture (REDCap) software.⁷² Surveys are sent via email and can be accessed through either a laptop, desktop or smart phone. Participants will also be called at day 2-3 (after urine culture results) and then weekly to assess issues with electronic materials. We will evaluate proportion of those with electronic success and investigate demographic variables that may be associated with inability to utilize electronic materials. To assess patient adherence to study procedures, defined as completion of all follow-up questionnaires, we will describe the percentage of enrollees who completed 100% of study procedures, 80% to 100% of study procedures and 50% to 80% of study procedure. A priori, we believe that compliance with 70% of study procedures will demonstrate satisfactory patient adherence to protocol. If the underlying adherence rate is 70%, a sample size of 70 provides a 10.1% MoE.

Exploratory Aim: To explore the safety of a culture-directed UTI treatment strategy and preliminary secondary outcomes of assigned treatments.

Safety Aims⁶²

1. Adverse events per group (most likely antibiotic side effects (i.e., gastrointestinal distress, antibiotic related diarrhea, rash) between groups.
2. Serious adverse events per group (defined in line with FDA reporting guidelines as a medical event that does one or more of the following: results in death, is life - threatening, requires inpatient hospitalization or prolongation of existing hospitalization, results in persistent or significant disability/incapacity, or is a congenital anomaly/birth defect.⁷⁷

Analysis. We anticipate that adverse events will be reported relatively infrequent.⁷⁸ All outcomes will be described using numbers and proportions of patients. Proportions between groups will be compared with either chi-square or Fischer's exact testing.

Secondary exploratory aims.

Proportion of those with clinical cure (as 2 or less points (slight, very slight, or no problems) on all five components of the UTISA (ref) at day 14 (***future trial primary outcome***)

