Analysis. All outcomes will be described using numbers and proportions of patients or means with confidence intervals. Proportions between groups will be compared with either chi-square or Fischer's exact testing and means will be compared with student's t-testing. Exploratory logistic regression modeling will be utilized to investigate the odds of both initial treatment failure and/or recurrent of UTI symptoms between groups and based on baseline characteristics

Power analysis:^{76,79} As above, we propose a future trial with a primary outcome to be symptom resolution at day 14 defined as 2 or less points (slight, very slight, or no problems) on all five components of the UTI symptom assessment (UTISA).^{43,78} The literature suggests 58-80% of women receiving empiric antibiotics for patient reported UTI will achieve clinical cure by day 3-7 after treatment initiation.^{43,78} Given that only women

with a positive urine culture will be given culture-directed antibiotics, and women in the empiric arm may have to have their antibiotics changed or stopped at the time of culture result, we anticipate a higher proportion of those in the culture-directed arm to have symptom resolution at day 7. Assuming 70% symptom resolution in the empiric arm, a future trial of 262 participants, with 131 per arm, would have 80% power to detect a 15-percentage point difference between groups with a 2-sided alpha of 0.05, while a sample size of 300 would be required assuming 65% resolution. Therefore, we believe that successfully recruiting a total of 70 participants at a rate of 6-7 participants/month will confirm the feasibility of future trial completion in <4 years (equivalent to other trials of antibiotic regimens for symptomatic UTI).^{17,78}

Statistical methods

Primary Outcomes	Statistical analysis
Feasibility: 
 - Number of subjects that were screened for participation - Number and proportion of subjects screened who met inclusion/exclusion criteria - Number and proportion of subjects who either declined participation or were ineligible (including reasons for ineligibility) - Number and proportion of eligible subjects that were enrolled in the study - Number and proportion of subjects enrolled who completed the study - Monthly enrollment rate 	Descriptive analysis = counts and proportions or means with standard deviation

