Adherence: 
 - Number of those that completed all study procedures - Number of subjects that took alternative agents taken by subjects for management of symptoms - Number of subjects in the culture-directed arm that acquired off-protocol antibiotics for their symptoms - Number of subjects able to complete electronic surveys 	Descriptive analysis = counts and proportions
Secondary Outcome	
Proposed primary outcome for future trial (Clinical Success at 14 days UTISA 1-3,5<=1)	Descriptive analysis = counts and proportions Comparative = Chi-square

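### The adherence measure does not show whether the day-14 UTISA can be collected, and the under-4-years conclusion rests on recruitment rate with no stated allowance for missing day-14 data

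*Combined protocol and SAP*

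**What the plan says.** D.1.1 makes adherence half of the primary outcome: "recruitment of 10% of eligible participants with 70% adherence to study protocol". The schedule there is "Participants will be sent electronic questionnaires after urine culture results and then weekly for a total of 4 weeks", and D.1.6 repeats the weekly contacts, with UTISA among the items. That makes one questionnaire after the culture result plus four weekly ones, so five; the documents do not print the total.

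In D.1.7, aim 1B, adherence is "defined as completion of all follow-up questionnaires, we will describe the percentage of enrollees who completed 100% of study procedures", followed by two bands for partial completion. The mark is worded as a share of procedures: "A priori, we believe that compliance with 70% of study procedures will demonstrate satisfactory patient adherence to protocol". The next sentence treats it as a rate among 70 people: "If the underlying adherence rate is 70%, a sample size of 70 provides a 10.1% MoE". The adherence rows of the statistical methods table include "Number of those that completed all study procedures".

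For the definitive trial, the power analysis states: "we propose a future trial with a primary outcome to be symptom resolution at day 14". It gives 262 women (131 per arm, 70% resolution in the empiric arm, a 15-point difference, 80% power, two-sided 5%) or 300 women if resolution is 65%. It infers completion in under 4 years from recruiting 70 women at 6-7 per month. No allowance for missing outcomes is stated.

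**The concern.** Whether the definitive trial can be completed on time depends on two rates: how fast women are randomised, and what share of them provide the day-14 outcome. The plan sets a target for the first and draws its timeline from it. For the second it has only a measure taken over the whole questionnaire schedule.

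That measure can move independently of day-14 completion. A woman who returns day 14 but misses week 4 has not completed all questionnaires. A woman who returns four of five but misses day 14 has completed 80% of them, which is above 70%. On either reading of the mark, the result does not say how often the proposed primary outcome was obtained.

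At stake is the pilot's conclusion about the next trial: it could report feasibility in under 4 years when the number to be enrolled would take longer. Full completion cannot be assumed. In the team's own earlier cohort (section B.2), 78 of 122 expectantly managed women (63.9%) completed the follow-up questionnaires. That was an observational study, so the figure is a caution and not a forecast.

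**Working it through.** **1. The plan's own figures.** Fisher's exact test has power 80.1% at 131 per arm (70% v 85%) and 80.3% at 150 per arm (65% v 80%). Both sample sizes therefore reproduce with nothing added for missing data. Months at 6.5 per month: 262/6.5 = 40.3 and 300/6.5 = 46.2. Both are under 48, so the timeline reproduces if every woman is evaluable. At 6 per month, 300/6 = 50 already exceeds 48.

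**2. Day-14 completion needed to finish in 48 months.** Required completion = evaluable N / (48 × monthly rate).

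| Rate per month | Enrolled in 48 months | For 262 evaluable | For 300 evaluable |
|---|---|---|---|
| 6 | 288 | 262/288 = 91% | not reachable |
| 6.5 | 312 | 262/312 = 84% | 300/312 = 96% |
| 7 | 336 | 262/336 = 78% | 300/336 = 89% |

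**3. Enrolment and duration at assumed completion levels.** Enrolled = evaluable N / completion, rounded up; months at 6.5 per month.

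| Day-14 completion (assumed) | 262 evaluable | 300 evaluable |
|---|---|---|
| 90% | 292 women, 45 months | 334 women, 51 months |
| 80% | 328 women, 50 months | 375 women, 58 months |
| 70% | 375 women, 58 months | 429 women, 66 months |

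At 70%, 262 evaluable takes 375/7 = 53.6 to 375/6 = 62.5 months over the plan's range of rates.

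**4. What the adherence mark shows.** Assume 90% of women complete each questionnaire, day 14 included.
- *If 70% of women must complete all five:* with independent misses, 0.9^5 = 59% complete all five, and the chance of at least 49 of 70 is 3.9%. With misses correlated within women (beta-binomial, assumed ICC 0.2 and 0.5), 69% and 79% complete all five, and the chance is 50% and 97%.
- *If the mark means 70% of procedures:* 90% of questionnaires are done, so the mark is met. If it means 70% of women completing at least 70% of the five, that is four or more: 92% of women under independence and 87% at ICC 0.2-0.5, so the mark is met almost surely.

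The same 90% day-14 completion can thus go with missing or meeting the mark, depending on its unit and on how misses cluster.

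**5. Precision of a day-14 figure from this pilot.** With n = 70, 1.96 × √(p(1−p)/70) gives 10.7 points at 70%, 9.4 at 80%, 8.4 at 85% and 7.0 at 90%. An observed 85% has an interval of about 76.6% to 93.4%. For 262 evaluable that is 262/0.766 = 343 women (53 months) to 262/0.934 = 281 women (43 months). The 70% line also shows that the plan's stated 10.1% margin does not reproduce; it would need about 79 women.

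**The case against.** **Scoring the whole schedule suits aim 1B.** This stands. The aim is to test electronic surveys and adherence to procedures, and each survey also carries side effects, other remedies and adherence to arm. The all-questionnaire measure should stay.

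**Day-14 completion can be derived anyway.** This largely stands. Loss to follow-up with reasons, study completion and day-14 success counts are all planned. A reader might infer that the pilot cannot supply day-14 retention; the documents do not support that. The figure is unnamed, not unobtainable. However, study completion is not defined, and the day-14 success row states neither its denominator nor how missing forms count.

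**The pilot was not set up to measure retention.** This also stands. Its stated aims are recruitment, adherence, exploratory safety and outcomes, and qualitative work. But the plan does draw a timeline conclusion, and that conclusion needs the figure.

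**The pilot would not wrongly fail.** A reader might infer that the mark is definitely scored on all five questionnaires, so that the pilot would probably fail despite good day-14 data. The wording allows partial completion, and on that reading the failure scenario disappears. The 3.9% needs both the strict reading and independent misses, and weekly calls and telephone administration may reduce misses. Nor do the documents say that falling below 70% stops the programme; the power calculation in D.1.7 defines feasibility by recruitment alone.

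**The sample sizes may hold some slack.** An uncorrected chi-square calculation needs 121 and 138 per arm, so 131 and 150 would leave about 8% spare (10/131, 12/150). The documents do not say this was intended. If it was, the completion needed at 6.5 per month falls to 242/312 = 78% and 276/312 = 88%. At 70% completion, 242/0.7 = 346 women would still take 53 months.

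**Conclusion.** The concern holds as a gap between what is measured and what is concluded. The adherence measure, whose 70% mark has an ambiguous unit, does not show whether the day-14 UTISA can be collected. The under-4-years conclusion is drawn from recruitment rate alone, with no stated allowance for missing day-14 data.

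At 6.5 per month the conclusion needs about 84% day-14 completion for 262 evaluable women (78-91% at 7-6 per month) and about 96% for 300. At 70% completion, 262 evaluable means about 375 women and 58 months. These figures assume a constant recruitment rate, 262 and 300 as evaluable numbers, and simple inflation by 1/completion. The completion levels are illustrations, since the documents give none for day 14.

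The finding is not that the pilot will give a wrong stop or go decision.

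**What to change.** 1. In aim 1B, keep completion of all questionnaires and the bands, and state whether the 70% mark refers to women or to procedures.
2. Add to the feasibility outcomes in the statistical methods table the number and proportion of randomised women with a scorable day-14 UTISA, overall and by arm, with 95% CI. Reconcile the cure definition first: the text uses 2 or less on all five components, while the table uses items 1-3 and 5 at 1 or less. What counts as scorable depends on this.
3. In the power analysis, base the under-4-years conclusion on the future sample size divided by the observed day-14 proportion, and carry its confidence limits through to months. State whether 262 and 300 already include any allowance.
4. Do not transfer the 70% mark to day-14 completion. At 70% the timeline is already exceeded, so a pilot could pass while showing that the schedule is unattainable.

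The cost is wording and one table row, from data already collected. Estimates by arm will be imprecise: with 35 women, about ±12 points at 85% (1.96 × √(0.85 × 0.15/35) = 11.8). The one downside is that the timeline claim may become less favourable.

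### The 70% adherence threshold can be read as two different rules that can give opposite verdicts, and its stated margin of error should be 10.7%, not 10.1%

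*Combined protocol and SAP*

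**What the plan says.** D.1.1 (Overview and Design) defines the primary outcome as "recruitment of 10% of eligible participants with 70% adherence to study protocol" and does not say what the 70% is a percentage of.

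D.1.7, Specific aim 1B, then uses more than one unit:

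- Adherence is "defined as completion of all follow-up questionnaires", a yes/no status for each woman.
- The reporting plan is graded: "we will describe the percentage of enrollees who completed 100% of study procedures", then "80% to 100% of study procedures and 50% to 80% of study procedure".
- The threshold is a share of procedures: "A priori, we believe that compliance with 70% of study procedures will demonstrate satisfactory patient adherence to protocol".
- The precision statement is a proportion of women: "If the underlying adherence rate is 70%, a sample size of 70 provides a 10.1% MoE".

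The statistical methods table lists adherence under the primary outcomes and counts women who completed all procedures, without a threshold. The power calculation for aim 1A names only the 10% recruitment target as the primary outcome.

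The follow-up schedule is given in D.1.1 ("Participants will be sent electronic questionnaires after urine culture results and then weekly for a total of 4 weeks") and D.1.6 ("Follow-up assessments will be completed weekly for a total of 4 weeks"). This can be read as five questionnaires (day 2-3 plus four weekly) or as four.

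**The concern.** A pass mark set in advance works only if its unit and denominator are also set in advance. Two rules can be drawn from aim 1B:

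- **Rule 1:** at least 70% of enrolled women complete all follow-up questionnaires. No single sentence says this. It follows from the definition together with the margin's n = 70, and it agrees with the count in the table.
- **Rule 2:** compliance with 70% of procedures. The plan does not say whether this is pooled over women or applied within each woman, or, if within each woman, how many must reach it.

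Judging whether a larger trial is feasible is the main product of this pilot. If nobody has said which figure decides, the same completion data could be reported as satisfactory or unsatisfactory. The margin quoted beside the threshold also does not follow from its own inputs.

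**Working it through.** **1. The margin.** Inputs from aim 1B: p = 0.70, n = 70. The 95% level is the one stated for the feasibility outcomes in aim 1A.

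- 1.96 × √(0.70 × 0.30 / 70) = 0.1074, or 10.7%. The stated 10.1% is not reproduced.
- Half-widths by other methods for 49/70: Wilson 10.5%, Agresti-Coull 10.6%, Jeffreys 10.6%, exact 11.3%. None gives 10.1%.
- A finite population correction is not declared. With the plan's own pool of 800 eligible women it gives 0.1074 × √(730/799) = 0.1026, or 10.3%.
- Without a correction, 10.1% needs n = 0.21 × (1.96/0.101)² ≈ 79 women.

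**2. Can the two rules disagree?** Here procedures are taken to mean follow-up questionnaires, as aim 1B's definition suggests.

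- Five questionnaires: 42 women complete 5/5 and 28 complete 4/5. Complete all: 42/70 = 60%, which fails rule 1. Every woman is at 80% or more, and the pooled share is (210 + 112)/350 = 92%, so rule 2 is passed however it is read.
- Four questionnaires: 42 women complete 4/4 and 28 complete 3/4. Complete all: again 60%. Every woman is at 75% or more, and the pooled share is (168 + 84)/280 = 90%.
- Rule 2 is itself ambiguous. If 42 women complete 5/5 and 28 complete 3/5, the pooled share is (210 + 84)/350 = 84%, but only 60% of women reach 70%.

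The conflict runs one way. If 70% of women complete everything, at least 70% of questionnaires are done, so data that pass rule 1 also pass rule 2.

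**3. When would they disagree?** The plan gives no model, so these are assumptions: a beta-binomial with completion probability p per questionnaire and within-woman correlation ρ, and rule 2 requiring the same 70% of women to reach at least 70% of questionnaires (4/5 or 3/4). For K questionnaires and ρ > 0, let S = (1 − ρ)/ρ and a = pS. The share completing all is the product of (a + j)/(S + j) for j = 0 to K − 1. At ρ = 0 it is p^K.

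Examples with K = 5 and p = 0.90:

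- ρ = 0: 0.9⁵ = 0.590 complete all. Adding 5 × 0.9⁴ × 0.1 = 0.328 gives 0.919 at 4/5 or better.
- ρ = 0.3: S = 2.333 and a = 2.1, so 0.900 × 0.930 × 0.946 × 0.956 × 0.963 = 0.729 complete all.

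| Questionnaires | p | Complete all, ρ = 0 / 0.3 | At least 70%, ρ = 0 / 0.3 |
|---|---|---|---|
| 5 | 0.90 | 59.0% / 72.9% | 91.9% / 86.9% |
| 5 | 0.85 | 44.4% / 61.7% | 83.5% / 79.8% |
| 4 | 0.90 | 65.6% / 75.7% | 94.8% / 89.6% |
| 4 | 0.85 | 52.2% / 65.3% | 89.0% / 83.7% |

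- At p = 0.90 the rules disagree in expectation when ρ is below about 0.22 (five) or 0.11 (four). At p = 0.85 the limits are about 0.51 and 0.44.
- At ρ = 0 they disagree for p between 0.782 and 0.931 (five) or 0.728 and 0.915 (four).
- At p = 0.95 both pass: at ρ = 0, 77.4% (five) or 81.5% (four) complete all.
- At p = 0.639 both fail. This is the only completion figure in the documents (78/122 in the observational cohort, B.2), applied here per questionnaire as an assumption. For ρ from 0 to 0.3, 10.7% to 28.1% complete all five and 40.7% to 49.6% reach 4/5. With four, the figures are 16.7% to 32.4% and 54.3% to 56.7%. The pooled 63.9% is also below 70%.

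**4. Do the planned bands settle it?** Partly. With five questionnaires, a within-woman 70% cut falls at 4/5 = 80%, a band edge, so the bands show it if exactly 80% is counted in the upper band. As written, exactly 80% falls in two bands, and so does exactly 100%. With four questionnaires the cut falls at 3/4 = 75%, which shares the 50% to 80% band with 2/4, so the bands do not show it.

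**The case against.** The best defence is that most of the text fits one rule. The definition, the adherence rate on 70 women and the table's count all point to the share of women completing everything, and one loosely worded sentence departs from that. This is fair as to the likely intent. But that sentence is the only explicit threshold in aim 1B, and a reader applying it literally reaches a different verdict.

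A second objection is that adherence may decide nothing. The aim 1A power calculation defines the primary outcome by recruitment alone, and the power analysis for the future trial says that recruiting 70 women at the planned rate will confirm feasibility. That inconsistency is real and should be removed. D.1.1 nevertheless puts adherence in the primary outcome, and the table lists it there.

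Third, study procedures could include the baseline questionnaires and the urine specimen in D.1.3.2, which would change the percentages above. This stands as a limit on the figures, and it is a further reason to define the unit. Five questionnaires is also the more natural reading, and the flow diagram, not available here, may settle the count.

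Fourth, the completion rates, correlations and model are assumed. They show where the rules part, not how likely that is. The 42/28 example needs no model.

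Finally, the margin error is 0.6 percentage points. It may come from a different denominator: a finite population correction with 600 women gives 10.1%, and the 2.4% recruitment margin also corresponds to 600 (1.96 × √(0.09/600) = 0.024; with 800 it is 2.1%). That is inference, and no pool of 600 is stated.

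**Conclusion.** The concern holds. The adherence part of the primary feasibility outcome has no single decision rule, and the rules that aim 1B supports can give opposite verdicts on the same data. The conflict occurs with four or with five questionnaires. Under the assumed model it covers per-questionnaire completion of roughly 0.73 to 0.93 when completion is independent, and narrows as within-woman correlation rises. Very high or low completion gives the same verdict under both rules. The all-complete count and the bands will disclose most of the data, so what remains open is which figure decides.

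The 10.1% margin is wrong for its printed inputs and should be 10.7%. This is a reporting error only, since n = 70 was set by resources. No hypothesis test, sample size or participant is affected. The point should still be fixed, because it concerns a primary success threshold.

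**What to change.** - State one rule, with unit and denominator, identically in D.1.1, aim 1B and the statistical methods table. For example: at least 70% of enrolled women complete all follow-up questionnaires, with the share of procedures completed reported descriptively.
- If a within-woman cut is intended instead, state the share of women who must reach it and report the count at that cut.
- State the number of follow-up questionnaires and what counts as a study procedure.
- Restate the margin as 10.7% and name the interval method.
- Make the bands non-overlapping: 100%, 80 to <100%, 50 to <80%, <50%.
- Make the primary-outcome sentence in the aim 1A power calculation agree with D.1.1.

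The cost is wording. The margin becomes slightly less favourable, and the sponsor gives up the freedom to choose the deciding figure after seeing the data. The change should be made before adherence data are reviewed.
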